7.9 Summary of risk mitigation strategies

The following risk mitigation strategies have been identified and will be implemented.

Table 8. Risk mitigation strategies

Individual risk	Risk evaluation	Identified risk mitigation strategies	Suggested implementation
Local allergic reaction	Low risk. No known allergen included.		Local corticoid cream or antihistaminic treatment for symptom relief
Anaphylactic reaction	Low risk. No known allergen included.	Exclusion of subjects with history of severe vaccine allergic reactions	Surveillance of all subjects on site for 30 minutes after immunization.
Strong / sustained inflammatory reactions	Low risk: low reactogenicity of pertussis antigens.	Paracetamol, NSAID	Monitoring (Day 7 phone call) + emergency phone numbers.
			Indications on use of paracetamol and NSAID for symptom relief
Direct pathogenicity of rPT	Low risk: reduced toxicity (by a factor of 10^5 - 10^6) compared to native PT	Exclusion of potentially vulnerable populations (young children, pregnant women, etc.)	None additional needed

8 STATISTICAL ANALYSIS

8.1 Sample size calculation

This is a phase II/III randomized, double-blind controlled study to compare the safety and immunogenicity of one compared to two doses of acellular pertussis vaccines including genetically-detoxified PT in adults previously immunized with chemically inactivated acellular pertussis vaccines. The sample size for this study is based on the previous study using the rPT vaccine in teenagers in Geneva (Blanchard [name] et al. CID 2019). Where applicable, 2-sided test at the 5% significance level will be utilized with no multiplicity adjustment. P-values will be considered exploratory only. One hundred volunteers will be randomized in total, with 50 in each group.

8.2 Safety analysis

The safety analysis will include all randomized subjects who have received a dose of study vaccine. The overall percentage of subjects with at least one spontaneously reported adverse event, with date of onset up to 28 days after vaccination will be tabulated with exact 95% confidence intervals, by type of adverse event; by severity; and by causality. They will be displayed by vaccine group as both frequencies and percentages on the ITT data set.

All reported adverse events that start post-vaccination will be tabulated. If a given disease is already reported as ongoing at the first visit on the medical history pages, it will be counted and tabulated as a vaccine emergent adverse event only if it worsens after the immunization with the study vaccine. Serious adverse events and discontinuation due to adverse event(s) will be described in detail by vaccine group.

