CLINICAL INVESTIGATORS:	[name], MD, PhD [name]
IMMUNOLOGICAL EVALUATOR:	[name], MD
EXTERNAL COLLABORATORS:	Collaborating immunology research laboratories
EXTERNAL MONITOR:	Center for Clinical Research (HUG)
NAME OF INVESTIGATIONAL PRODUCT:	Pertagen® (BioNet-Asia acellular pertussis vaccine)
NAME OF ACTIVE INGREDIENTS:	Genetically detoxified pertussis toxin (rPT) and filamentous hemagglutinin (FHA), alum adsorbed
INVESTIGATIONAL PRODUCT DOSAGE, SCHEDULE, AND MODE OF ADMINISTRATION:	
Product dosage:
 
Group 1: Pertagen® (BioNet-Asia): recombinant Pertussis Toxin (rPT) 5µg; filamentous hemagglutinin (FHA) 5 µg Revaxis® (Sanofi Aventis): tetanus toxoid, 20 UI; diphtheria toxoid 2 UI; inactivated polio viruses.
 
Group 2: Pertagen®
 
Schedule: One vaccination on Day 0 and 6 months later for each volunteer.
 
Group 1 will receive one dose of Revaxis® followed by 1 dose of Pertagen®.
 
Group 2 will receive two doses of Pertagen®.
 
A dose of Revaxis® will be offered at the last visit if useful for protection.
 
Mode of Administration: Intramuscular injection into the deltoid region of the upper extremity, using a syringe with a 1 to 1.5 inch #25-gauge sterile needle.

PROTOCOL SYNOPSIS – PHASE II/III 2 doses rPT-VACCINE TRIAL	
TRIAL DESIGN:	Phase II/III, randomized, double-blind controlled trial
STUDY POPULATION:	Adults aged 18-30 years previously primed with acellular pertussis vaccines (see entry criteria below).
SAMPLE SIZE:	100 volunteers
FOLLOW-UP PERIOD:	6 months following the second injection
STUDY PERIOD:	July 2021 – September 2023

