2.2 Secondary objectives

- To assess the safety of two doses at 6 months interval of intramuscular immunization with Pertagen® administered to adults, compared to one dose of Pertagen®.
- To assess the humoral responses elicited by two doses of Pertagen® when administered to adults, compared to one single dose.

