4.2.3 Compliance with dosing regimen

The first intervention (study vaccine Pertagen® or Revaxis®) will be administered by the Clinical Investigator at Day 0, and the second (Pertagen®) at Day 180. At no time will the study medication be in the possession of the volunteer; compliance will not, therefore, be an issue.

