4.3 Randomization

At Day 0, eligible subjects will be randomized in a 1:1 ratio into one of the following vaccine groups:

Group A	Revaxis® + Pertagen®	50 subjects
Group B	Pertagen® + Pertagen®	50 subjects

Table 1. Study groups

Randomization procedure

Randomization allocation will be performed on a 1:1 basis generated by computer randomization, with a 10-block size, concealed in sequentially labeled opaque envelopes. Each participant will be assigned a unique treatment number that corresponds to his or her treatment allocation. Only the unblended immunizing nurses will have access to the treatment allocation.

Randomization of subjects to treatment will occur at Visit 1 after all entry procedures have been performed and eligibility for the study confirmed. 100 volunteers will be allocated to either Group A or Group B at the ratio of 1:1 and will receive a 3-digit subject number preceded by the acronym of the study site (GE- _ _). The 3-digit subject number will be assigned according to the participant's chronological order of enrollment at the site. The subject number will be used as the subject identifier throughout the study.

Each participant will be randomized following the randomization list by chronological order and will be immunized according to the vaccine group assignment.

Participants will be blinded in order to keep the double-blind design of the study.

The personal responsible for study vaccine preparation, handling, storage and accountability, as well as immunization will be unblinded.

The team responsible for assessing adverse events will be blinded.

The laboratory staff performing the immunological assays will also be blinded.

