6.3 Procedures for handling subjects with premature study discontinuation

In the absence of a medical contraindication or significant protocol violation, every effort will be made by the Investigator to keep the subject in the study. If a subject has to be withdrawn, all efforts will be made to complete and report the trial observations as thoroughly as possible. If a subject needs to be withdrawn, all efforts shall be made to follow safety of the subject as per protocol.

Subjects who withdraw or are withdrawn from the study prior to treatment application will be replaced. No follow-up of these subjects will be performed and no data will be analyzed. Subjects withdrawing or withdrawn after treatment application will not be replaced if study recruitment has already been terminated, and their data will be analyzed under the intention-to-treat (ITT) principle.

When a subject withdraws from the study before the planned end of the study period, all investigations scheduled for the end-of-study visit should be performed if the subject agrees. End-of-study evaluation will be completed at the time of the subject's withdrawal, with an explanation of the reason for this entered onto the respective "end-of-study" section of the CRF as follows:

- Adverse event (specify);
- Death;
- Protocol violation (specify);
- Medical condition (specify);
- Consent withdrawal, not due to AE;
- Other (specify).

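### Section 8.2 tabulates adverse events by randomized group with no per-injection denominator, so anyone who misses the Day 180 injection or gets the wrong Visit 1 vaccine is counted under a regimen not received

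*Combined protocol and SAP*

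**What the plan says.** Section 8.2 first sets an inclusion rule: "The safety analysis will include all randomized subjects who have received a dose of study vaccine". It then asks for the overall percentage of participants with any spontaneously reported event starting within 28 days of vaccination, with exact 95% intervals, by type, severity and causality. Of these results it says: "They will be displayed by vaccine group as both frequencies and percentages on the ITT data set".

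Four other places determine what that means in practice.

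- Section 4.3 uses the term vaccine group for the randomized allocation: "eligible subjects will be randomized in a 1:1 ratio into one of the following vaccine groups".
- Section 6.3 says of people who leave after treatment that "their data will be analyzed under the intention-to-treat (ITT) principle".
- The synopsis gives the sequences, where Groups 1 and 2 correspond to Groups A and B elsewhere: "Group 1 will receive one dose of Revaxis® followed by 1 dose of Pertagen" and "Group 2 will receive two doses of Pertagen". Group A therefore gets its only Pertagen at Day 180.
- Section 4.2.3 treats both products as study vaccine: "The first intervention (study vaccine Pertagen® or Revaxis®) will be administered by the Clinical Investigator at Day 0".

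The safety objective in section 2.2 compares two doses with one. It begins "To assess the safety of two doses at 6 months interval of intramuscular immunization with Pertagen" and names one dose of Pertagen as the comparator.

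**The concern.** The safety question is about exposure: what happens after one Pertagen dose and after two. The table is arranged by allocation. The two agree for anyone who receives both assigned injections. They part for anyone who does not return for Visit 3 and for anyone given the wrong syringe at Visit 1.

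As the analysis is descriptive, the displayed percentages are the result, and their denominators decide what they mean. A person who never had the second injection cannot have an event after it, yet remains in the only denominator the plan provides. Tabulating by causality also presupposes that events are attached to the vaccine actually given.

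**Working it through.** **Step 1: who is misplaced.** Reading 8.2 with 4.3, 6.3 and 4.2.3:

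| Participant | Received | Column in 8.2 |
|---|---|---|
| Group A, completes | Revaxis, Pertagen | Group A, correct |
| Group B, completes | Pertagen, Pertagen | Group B, correct |
| Group A, leaves before Day 180 | Revaxis only | Group A (one-dose arm), if Revaxis is study vaccine |
| Group B, leaves before Day 180 | one Pertagen | Group B (two-dose arm) |
| Wrong vaccine at Visit 1 | the other group's product | group as randomized |

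The requirement of one dose in 8.2 does not resolve this. It removes only people never injected, whom 6.3 already replaces and leaves out of the analysis. A mix-up between the two products matters only at Visit 1, because both groups are assigned Pertagen at Visit 3.

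**Step 2: inputs for the size.** The plan gives no safety figure to reproduce. Section 8.1 gives 50 per group. Neither the event risk nor retention is stated, so both are assumptions here: risk p per injection of 20% or 40%, independent between injections, and m of 50 missing the second injection, from 0 to 15. The upper value is the difference between 50 randomized and the 35 per group that the synopsis says are needed for immunogenicity. The protocol does not call that difference a dropout allowance, so 15 is an outer illustration and not a forecast.

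**Step 3: formulas.**

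- Any event over the study, as 8.2 specifies: [(50 − m)(1 − (1 − p)²) + m·p] / 50. An early leaver still contributes the first injection.
- Event after injection 2 on the same denominator: (50 − m)·p / 50. Section 8.2 does not ask for this rate. It is what a reader would get by splitting the table by injection without changing the denominator.

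With p = 0.40, those who receive both injections have 1 − 0.6² = 64%. With m = 5: (45 × 0.64 + 5 × 0.40)/50 = 30.8/50 = 61.6%. With m = 15: (35 × 0.64 + 15 × 0.40)/50 = 28.4/50 = 56.8%. After injection 2: 0.40 × 45/50 = 36% and 0.40 × 35/50 = 28%.

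| m of 50 | Any event, p = 40% | After injection 2, p = 40% | Any event, p = 20% | After injection 2, p = 20% |
|---|---|---|---|---|
| 0 | 64.0% | 40.0% | 36.0% | 20.0% |
| 5 | 61.6% | 36.0% | 34.4% | 18.0% |
| 10 | 59.2% | 32.0% | 32.8% | 16.0% |
| 15 | 56.8% | 28.0% | 31.2% | 14.0% |

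**Step 4: against the precision of the trial.** Exact 95% intervals for the rate after injection 2 at p = 20%: with m = 5, 9/50 = 18% (8.6 to 31.4) against 9/45 = 20% (9.6 to 34.6); with m = 15, 7/50 = 14% (5.8 to 26.7) against 7/35 = 20% (8.4 to 36.9). The shift lies well inside the sampling error. One wrong-vaccine case moves a group's percentage by at most about 1/50 = 2 points.

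**The case against.** Several points on the other side stand.

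- The problem is conditional. It affects only people who miss Visit 3 or receive the wrong Visit 1 vaccine, and with high retention it could be negligible.
- The wording on study vaccine is not uniform. Section 3.1 calls Pertagen the study vaccine and Revaxis the control, and 12.1 uses the term for Pertagen. On that reading a Group A participant who never had Pertagen falls outside the safety set, and the Group A half of the point disappears. Section 4.2.3, and the heading of 3.1, which covers both products, point the other way. The Group B half holds on either reading.
- The columns are regimens, and everyone in the set has been injected at least once.
- The sentence at issue governs spontaneously reported events. Solicited reactions are only said, in the synopsis, to be described by treatment group, with no analysis set named.

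A reader might infer more: that the plan conceals reactions to Pertagen, or that its table would show 36% or 28% where the truth is 40%. The documents do not support either. Section 8.2 tabulates every event that starts after vaccination and describes serious events and discontinuations for adverse events in detail, so no event is removed. The 36% and 28% belong to a rate after injection 2, whereas 8.2 specifies an any-event percentage, which moves less. Nor is the direction certain: section 6.2 allows withdrawal for an adverse event, and keeping such people in the table raises the any-event rate.

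The descriptive nature of the analysis does not answer the point. It means that no test is affected, but the percentages are still what will be read.

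**Conclusion.** The point holds as a defect in a stated rule. Section 8.2 groups by allocation on an undefined data set, offers no as-received grouping and no per-injection denominator, and nothing elsewhere corrects this. Early leavers and wrong-vaccine cases are therefore shown under a regimen they did not receive, in a table meant to compare one Pertagen dose with two.

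The size is unknown. At an assumed 40% risk per injection with independence, the specified any-event percentage falls by 2.4 points with 5 of 50 missing the second injection and by 7.2 points with 15. At 20% risk the falls are 1.6 and 4.8 points. A rate after injection 2 on the same denominator would fall by 4 and 12 points, or by 2 and 6. The Group A part also rests on Revaxis counting as study vaccine. The matter is one of interpretation, inexpensive to settle before the tables are programmed.

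**What to change.** In 8.2, replace the reference to the ITT data set with a defined safety set: everyone who received at least one injection of either product, grouped by the vaccine or vaccines actually received. Tabulate solicited and unsolicited events separately after each injection, using the participants who received that injection as the denominator. State in 8.2 that Revaxis counts as study vaccine for this purpose, so that 3.1, 4.2.3 and 12.1 no longer leave it open.

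Keep the overall display by randomized group as supplementary. It is still useful, because those who return for the second injection are a selected subset and the table after injection 2 is not a strictly randomized comparison.

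The cost is a sentence or two in 8.2 and minor extra table programming. Events are already collected for 28 days after each vaccination (4.4) and administration is logged (3.4), so no new data are needed.

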8.3 Immunogenicity analyses

The primary immunogenicity endpoint will assess the immune response to two doses of Pertagen®, as compared to one dose, by measuring the Day 28 geometric mean concentration (GMC) of neutralizing antibodies to PT after immunization.

The other immunogenicity end-points are listed in Section 2.2 of this protocol.

The following descriptive statistics will be provided for each variable: number of subjects, percentages, mean, geometric mean, standard deviation, median, minimum, maximum, and range.

Immunogenicity endpoints and confidence bounds will be calculated for each group and compared (using Chi-square or Fisher's exact test for binary endpoints, and Wilcoxon-Mann-Whitney's test or Kruskal-Wallis test for quantitative endpoints). All tests will be two-sided.

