RATIONALE:	
A significant increase of pertussis incidence is reported in a growing number of countries. This resurgence is considered as resulting from the limited durability of aP-vaccine-induced immunity and is associated with increased mortality in young infants and morbidity at all age groups. As the pertussis immunity acquired through immunization or infection is short-lived, its maintenance or reactivation requires repeat boosting at regular time points. Thus, novel strategies capable of reactivating pertussis immunity are needed.
 
The efficacy of current acellular pertussis vaccines (which contain chemically-detoxified pertussis toxoid (PT)) rapidly wanes, in part because priming and repeat immunization with acellular vaccines induce antibodies specific for the chemically-detoxified PT but unable to efficiently recognize the native PT expressed by B. pertussis.
 
Clinical studies have shown the superior immunogenicity profile of acellular pertussis vaccines including genetically-detoxified PT (rPT) in adults and adolescents previously primed with aP. In particular, we showed in a past Geneva study in teenagers previously primed with aP that rPT/FHA induced a stronger recall response than the current aP-vaccine at one month post-vaccination. However, the difference was less clear one year after vaccination, suggesting that 2 doses may be needed for more sustained immunity.
 
In the present study, we would like to assess whether giving two doses of rPT/FHA at 6 months interval induces stronger immune responses than a single dose.

PRIMARY OBJECTIVE:	
To assess B cell responses to two doses compared to one dose of an acellular pertussis vaccine (Pertagen®) including genetically detoxified pertussis toxin (rPT) when delivered by the intramuscular route to adult volunteers previously primed and boosted with chemically-detoxified PT.
 
 The primary endpoint will be the geometric mean concentration (GMC) of anti-PT neutralizing antibodies assessed 4 weeks (early immunity) and 6 months (sustained immunity) following one or two injections of Pertagen® given at 6 months interval.

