Inactivated polio viruses type 1-2-3	-	40U (type 1), 8U (type 2), 32U (type 3)
Adjuvants		
Aluminum Hydroxide	0.3 mg/dose	0.35mg/dose
Volume for Injection	q.s. to 0.5 mL	q.s. to 0.5 mL
a: Recombinant Pertussis Toxin (rPT)		

Table 2. Composition of each dose of 0.5mL presented in pre-filled syringe

Visit 1: Randomized participants will receive one dose of Revaxis® (Group A) or one dose of Pertagen® (Group B) by intramuscular injection in the deltoid. All volunteers will be observed at the Plateforme de Recherche Clinique PGO for 30 minutes after immunization.

Diary cards will be distributed to study volunteers to record post-immunization local and systemic reactions avec adverse events. Volunteers will complete daily diaries for 7 days after immunization.

All volunteers will be followed for 28 days after immunization and all adverse events will be collected and monitored for 28 days after vaccination.

Visit 2: At Day 28, a second visit will take place for safety evaluation, blood draw and revision of diary cards. Investigators will reconcile and transcribe the Diary Card information in the CRF.

Visit 3: At 6 months, a third visit will take place for the second vaccination. Randomized participants will all receive one dose of Pertagen® (Groups A and B) by intramuscular injection in the deltoid. All volunteers will be observed at the Plateforme de Recherche Clinique PGO for 30 minutes after immunization.

Diary Cards will be distributed to study volunteers to record post-immunization local and systemic reactions and adverse events. Volunteers will complete daily diaries for 7 days after immunization.

All volunteers will be followed for 28 days after immunization and all adverse events will be collected and monitored for 28 days after vaccination.

Visit 4: At Day 28 post second immunization, a 4th visit will take place for safety evaluation, blood draw, and revision of diary cards. Investigators will reconcile and transcribe the Diary Card information in the CRF.

Visit 5: A final visit will take place at 6 months post-second immunization (blood draw).

At this visit, Group 2 participants will be offered one dose of Revaxis® if needed for their protection (last dose of tetanus-containing vaccine \geq 10 years).

Blood draws performed on Day 0 (Baseline), Day 28, and Month 6 following each vaccination will be used to evaluate early and sustained vaccine responses.

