The primary statistical analysis will be based upon visit 4 and visit 5 data to compare the early and sustained immunogenicity of one or two doses of Pertagen®.

PROTOCOL SYNOPSIS – PHASE II/III 2 doses rPT-VACCINE TRIAL

**SUBJECT INCLUSION
CRITERIA:**

- Has provided written informed consent;
- Male or female, ages 18 to 30 years (inclusive) at the time of enrollment;
- With documented history of acellular pertussis immunization (5 doses);
- Free of clinically significant health problems, as determined by pertinent medical history and clinical examination at study screening;
- Non-pregnant, non-lactating females :
 - A negative urinary pregnancy test at enrollment;
 - If sexually active, female subjects must be willing to use reliable birth control measures for 1 month after each vaccination;
- Able to attend all scheduled visits during one year and to understand and comply with the study procedures;

**SUBJECT EXCLUSION
CRITERIA:**

- Prior dTpa immunization within the last 5 years or prior dT immunization within the last 2 years, or any other investigational vaccine likely to impact on interpretation of the trial data;
- Suspected or confirmed pertussis infection within the last 10 years or documented pertussis infection in a household member within the last 10 years;
- History of severe local or systemic reactions to any vaccination;
- Known hypersensitivity or allergy to diphtheria, tetanus, or pertussis-containing vaccines (including excipients);
- Receipt of investigational product up to 30 days prior to enrollment or ongoing participation in another interventional clinical trial;
- Receipt of licensed vaccines within 30 days of planned study immunization or ongoing participation in another clinical interventional trial likely to interfere with study results;
- Acute or chronic, clinically significant psychiatric, hematologic, pulmonary, cardiovascular, or hepatic or renal functional abnormality as determined by the Investigator based on medical history and physical exam;
- Any confirmed or suspected immunosuppressive or immunodeficient condition, including human immunodeficiency virus (HIV) infection, asplenia, cytotoxic therapy in the previous 5 years, and/or diabetes;
- Has a known history of vaccine-induced Guillain-Barré Syndrome;
- Has an active malignancy or recent (<10 years) history of metastatic or hematologic malignancy;
- Suspected or known alcohol and/or illicit drug abuse within the past 5 years;

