2.1.1 Primary outcome measures

The main immunogenicity endpoints will be the geometric mean concentration (GMC) of neutralizing antibodies to PT.

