5.1.3 Visit 2 (Day 28 +7)

Study participants will be contacted by phone or mail a few days before Visit 2 to confirm the appointment and be reminded of the need to bring the diary card.

The following activities will be performed during Visit 2:

- The diary card on solicited and unsolicited AEs, SAEs and concomitant medications will be discussed, verified and collected;
- AEs and SAEs will be recorded;
- 29 mL of blood will be collected from all subjects for:
 - Complete blood count;
 - Anti-PT and anti-FHA IgG antibodies by ELISA;
 - Anti-diphtheria and anti-tetanus IgG antibodies by ELISA;
 - Anti-PT neutralizing IgG;
 - Ficoll isolation and freezing of PBMC with preservation and freezing of plasma aliquots;
- The appointment for Visit 3 (Day 180) will be confirmed.

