5.1.6 Visit 4 (Day 210 +7)

Study participants will be contacted by phone or mail a few days before Visit 4 to confirm the appointment and be reminded of the need to bring the diary card.

The following activities will be performed during Visit 4:

- The diary card on solicited and unsolicited AEs, SAEs and concomitant medications will be discussed, verified and collected;
- AEs and SAEs will be recorded;
- 29 mL of blood will be collected from all subjects for:
 - Complete blood count;
 - Anti-PT and anti-FHA IgG antibodies by ELISA;
 - Anti-diphtheria and anti-tetanus IgG antibodies by ELISA;
 - Anti-PT neutralizing IgG;
 - Ficoll isolation and freezing of PBMC with preservation and freezing of plasma aliquots;
- The appointment for Visit 5 (Day 365) will be confirmed.

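### The synopsis makes the neutralizing anti-PT GMC primary at Visits 4 and 5, but Section 8.3 makes only an unanchored Day 28 GMC primary, so the 6-month result has conflicting status

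*Combined protocol and SAP*

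**What the plan says.** Four places in the combined protocol and SAP define the primary endpoint.

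- **Synopsis, Primary objective.** The primary endpoint is the GMC of anti-PT neutralizing "antibodies assessed 4 weeks (early immunity) and 6 months (sustained immunity) following one or two injections of Pertagen".
- **Synopsis, Procedure and follow-up.** "The primary statistical analysis will be based upon visit 4 and visit 5 data to compare the early and sustained immunogenicity".
- **Section 2.1.1.** "The main immunogenicity endpoints will be the geometric mean concentration (GMC) of neutralizing antibodies to PT". No time point is given.
- **Section 8.3.** The response to two doses is compared with the response to one "by measuring the Day 28 geometric mean concentration (GMC) of neutralizing antibodies to PT after immunization". The injection is not named, and the other immunogenicity endpoints are referred to Section 2.2.

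Section 2.2.2 lists GMCs for ELISA IgG only. Neutralizing antibodies appear there only as seroresponse rates, and the synopsis's list of secondary objectives likewise has no neutralizing GMC.

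The synopsis justifies 35 volunteers per group by 90% power for a doubling of neutralizing PT antibodies after two doses compared with one. It does not say at which visit. Section 8.1 sets two-sided 5% tests, makes no multiplicity adjustment and calls all p-values exploratory.

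**The concern.** An analyst who follows the synopsis reports two primary results. One who follows Section 8.3 reports one. Nothing in the document says which text prevails.

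The result in dispute is the important one. The synopsis rationale is that the advantage seen in the earlier Geneva study of teenagers was less clear after a year, and that a second dose might sustain it. The 6-month neutralizing GMC tests that idea directly. Suppose the groups differ at Visit 4 but not at Visit 5. Under 8.3 the trial has a positive primary result, and the sustained result has no declared rank. Under the synopsis both results must be reported as primary. The document allows that choice to be made after the data are known.

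A lesser problem is the label. In the visit schedule Day 28 is Visit 2, before anyone has had a second injection.

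**Working it through.** This is mainly a comparison of texts.

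**Step 1. Status of each neutralizing anti-PT GMC**

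| Source | Visit 4 | Visit 5 |
|---|---|---|
| Synopsis | primary | primary |
| Section 2.1.1 | main endpoint, time not stated | main endpoint, time not stated |
| Section 8.3 | primary, if Day 28 means after the second injection | not primary; referred to Section 2.2 |
| Section 2.2.2 | not listed | not listed |

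Section 2.1.1 is compatible with the synopsis. Sections 8.3 and 2.2.2 taken together are not.

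**Step 2. What each visit compares**

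At Visit 1, Group A receives Revaxis and Group B receives Pertagen. At Visit 3 both receive Pertagen (synopsis, Procedure and follow-up).

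| Visit | Scheduled day | Pertagen doses, B versus A |
|---|---|---|
| 2 | 28 | 1 versus 0 |
| 4 | 210 | 2 versus 1 |
| 5 | 365 | 2 versus 1 |

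Counted from the second injection at Day 180, Visit 4 falls nominally at 210 − 180 = 30 days and Visit 5 at 365 − 180 = 185 days. The protocol uses Day 28 for both injections: Section 2.2.2 does so, and the synopsis says "Visit 4: At Day 28 post second immunization, a 4th visit will take place". The label alone therefore does not identify the visit.

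**Step 3. Why the visit behind the power statement matters (illustration only)**

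The document gives no SD, so the figure of 35 per group cannot be reproduced independently. The formula can only be solved for the SD that the figure implies, using 35 per group, 90% power, a 2-fold ratio and two-sided 5%:

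SD = log10(2) / [(1.960 + 1.282) × √(2/35)] = 0.388 on the log10 scale.

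With 50 per group, the standard error of the difference is 0.388 × √(2/50) = 0.078, and power = Φ(log10(ratio)/SE − 1.960).

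| True ratio | Normal approximation | t-test | Wilcoxon-Mann-Whitney (4,000 simulations) |
|---|---|---|---|
| 2.0 | 97.2% | 97.0% | 96.1% |
| 1.75 | 87.9% | 87.2% | 85.1% |
| 1.5 | 62.0% | 61.2% | 58.8% |

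These figures assume log-normal titres, the same SD at both visits and no loss to follow-up. The ratios of 1.75 and 1.5 are assumptions, not document figures. A sample size sufficient for a 2-fold ratio at Visit 4 may not be sufficient at Visit 5 if the ratio is smaller there.

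**Step 4. One or two primary tests**

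One test at 5% has a 5% error rate. Two unadjusted tests, with success on either, have 1 − 0.95² = 9.75% if independent. With an assumed correlation of 0.5 to 0.9 between visits the rate is about 9.1% to 7.0%. This matters only if a confirmatory claim is made, and Section 8.1 makes none.

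**The case against.** The strongest case against has four parts.

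1. **The 1-versus-0 reading is not really open.** Section 8.3 speaks of two doses compared with one, and that contrast does not exist at Visit 2. This largely stands: the intended visit is almost certainly Visit 4. The text should still name it. Reading 8.3 as Visit 4 also leaves the main conflict in place, because 8.3 then has one primary time point and the synopsis has two.

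2. **The Visit 5 GMC is not lost.** Section 2.1.1 covers it in general terms, the synopsis endpoint row includes antibody responses at Month 6 after the second injection, and Section 5.1.7 schedules the sample. This is true, so the measurement is planned. None of these places gives it a rank, however, and rank is what is in dispute.

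3. **All p-values are exploratory, so no error rate depends on the label.** This is correct, and it limits the consequence to which result is presented as primary. It does not settle that question in a protocol that names a primary endpoint and cites 90% power.

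4. **The power figures rest on a back-solved SD and assumed ratios.** They do. They illustrate why the power statement needs a visit, and the conclusion does not depend on them.

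A related point also stands. The synopsis puts Visit 4 at 28 days after the second injection, while Section 5.1.6 labels it Day 210, nominally 30 days after. With Visit 3 allowed at Day 180 ± 30 and Visit 4 at Day 210 + 7, counting both from Day 0 permits an interval of 210 − 210 = 0 to 217 − 150 = 67 days. This is a separate inconsistency, but it strengthens the case for counting from the second injection.

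**Conclusion.** The concern holds, with high confidence, and must be fixed before analysis. The synopsis and Section 8.3 cannot both be followed: the first has two primary time points and the second has one. If 8.3 and 2.2 govern, the 6-month neutralizing GMC is neither primary nor a named secondary endpoint, although it addresses the trial's reason for giving a second dose. The missing injection in 8.3 and the missing visit in the power statement are parts of the same fault.

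The conclusion rests on the current wording alone and needs no numerical assumption. Because p-values are declared exploratory, the harm is an open choice of headline result rather than an inflated confirmatory error rate.

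**What to change.** Use one definition in the synopsis, Section 2.1.1 and Section 8.3: neutralizing anti-PT GMC, Group B versus Group A, at Visit 4 (28 days after the second injection) and Visit 5 (6 months after it). This is the synopsis's own definition. In 8.3, replace the Day 28 phrase with these two visits, counted from the second injection. If the sponsor wants a single primary visit, name it and list the neutralizing GMC at the other visit explicitly in Section 2.2. State which visit the 90% power refers to. Reconcile the day labels in Sections 5.1.6 and 5.1.7 with the chosen definition.

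The p-values can stay exploratory, with early and sustained results reported separately and no confirmatory claim. If a confirmatory claim is wanted, state in advance how the two visits combine. That choice is the sponsor's.

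The cost is wording only. Blood for anti-PT neutralizing antibodies is already drawn at both visits (Sections 5.1.6 and 5.1.7), so no participants, visits or samples are added. Keeping the p-values exploratory costs no power.
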